Caregiver Participation Measures. Multiple measures and multiple informants will be used to assess caregiver participation in JDC weekly status hearings and treatment sessions. Caregiver attendance in JDC will be independently recorded by the JDC supervisors or research assistant using the Parent/Caregiver Drug Court Attendance Form and collected weekly at drug court. Differences between research assistants and supervisor reports will be reconciled using court records. Drug court records will also be reviewed for caregiver and youth attendance and unexcused absences at drug court sessions. Quality of caregiver participation in drug court will be recorded using the Juvenile Drug Court Caregiver Participation Ratings form, which will be completed by a research assistant. Barriers to Drug Court participation will be measured using the Barriers to Drug Court Participation measure, which will be completed by the caregiver. Similarly, caregiver attendance at youth treatment sessions will be recorded by therapists and measured as a percent of scheduled sessions using the Caregiver Contingency Management Session Tracking Sheet (CM Group) or Caregiver Treatment as Usual Session Tracking Sheet (Treatment as Usual Group); Barriers to Treatment participation will be measured using the Barriers to Treatment Participation measure, which will be completed by the caregiver. See the schedule of assessments table below for timing of assessment.

Implementation fidelity. The 12-item Contingency Management Competence Scale (CMCS) assesses fidelity to prize-based CM procedures. The CMCS has good inter-rater reliability, internal consistency, discriminant, concurrent and predictive validity in substance abusing outpatients. In the present study, the CMCS will be used to rate CCM audiotapes. Initially, 100% of audiotapes will be reviewed to establish inter-rater reliability. Subsequently, the CMCS will be used to assess treatment fidelity. Treatment implementation will also be measured using the Caregiver Contingency Management tracking sheet, which will be completed by the therapist. The Caregiver Contingency Management tracking sheet will track number of prize draws provided to families at each session and the associated activities. To maintain balance across the treatment groups, a comparable measure will be given to the treatment as usual group, Caregiver Treatment as Usual session tracking sheet.

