Refinement of intervention/assessment protocols. Research assistants will conduct semistructured exit interviews (Qualitative Interview- Caregiver, Qualitative Interview- Therapist, Qualitative Interview- Youth, Qualitative Interview- Drug Court) with the caregivers, youths, therapists, and JDC personnel to assess their perceptions of intervention components, study procedures, and suggestions for research and intervention refinement. Therapists and JDC personnel will be asked about their views of CCM during each year of clinical implementation. Youth and caregivers will be interviewed separately and asked about their general opinions of drug court and CCM procedures at the conclusion of treatment. Analysis of the qualitative exit interview data will inform the refinement of CCM in terms of intervention content and delivery and will be used to plan dissemination efforts. We will collect semi-structured exit interviews from a subset (20%, n=36; randomly selected throughout the study) of families regardless of intervention attendance or treatment success. All exit interviews will follow semi-structured interview guides and be conducted in accord with standard qualitative procedures (e.g., allowing the interviewer to elaborate on relevant and important issues that emerge during the interview). Interviews will be audio recorded, transcribed, and analyzed using grounded theory qualitative methods. Given the cyclical nature of data collection and analysis in qualitative research, the guides may change during data collection to incorporate questions raised by emerging themes and issues in the interviews. [name] (Co-I) will participate in developing the interviews and overseeing their analysis, drawing from her substantial experience conducting qualitative research using grounded theory methods and teaching qualitative methods of inquiry.

Control Measures. To control for the quality of the relationship with the therapist (CCM, TAU) as a potential confound, caregivers, youth, and therapists will complete the 36-item **Working Alliance Inventory** (WAI), which measures three aspects of the therapeutic alliance; emotional bond, agreement on goals, and agreement on tasks. The WAI will be completed monthly during active treatment. To assess and control for other services the youth may receive besides research treatment conditions the caregiver will be asked during the monthly assessments if the youth received mental health or substance abuse services beyond TAU.

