Model building & estimation. The data will be analyzed using MRMs. This approach provides a variety of options for modeling change over time, including linear, non-linear, and phase-specific (e.g., during-treatment, post-treatment) patterns of change. Prior to analysis, each outcome will be graphically and descriptively evaluated to determine the best distribution for modeling. The model building approach detailed by Singer and Willett will be used to specify fixed and random effects. First, a fully unconditional model will be estimated to determine the proportion of within- and between-subject outcome variance. Second, at the repeated measurements level, and informed by the spaghetti plots, growth terms (e.g., linear, quadratic) will be specified to explain the within-subject variance. These terms will be computed using participants' actual assessment dates, tailoring the model to the observed spacing of measurements. 100 Third, the effect of CCM will be modeled by an uncentered, dichotomous indicator (i.e., CCM = 1, TAU = 0) at youth/caregiver level (i.e., level-2), and cross-level interaction effects will be specified between the CCM indicator and the level-1 growth term(s). Before estimating the final model, fixed effect indicators will be included to test for systematic differences across therapists, providers, and districts/judges, and if identified, differences will be statistically controlled in the final model. The analyses will use an intention-to-treat approach, with youth/caregivers retained in the research measurement portion of the study independently of participation in the intervention. The models will be performed using HLM software. 101 Significance tests for variance components will be based on the likelihood ratio test, tests for fixed effects will be based on the Wald test (i.e., B / SE), and 95% CIs will be computed to reflect the magnitude and precision of the effects.

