Aim 1: Evaluate whether caregivers receiving prize incentives (CCM) for attendance and participation in JDC and adolescent drug treatment show greater attendance and participation in JDC and adolescent drug treatment relative to parents not receiving CCM (i.e., JDC TAU). The data for evaluating this aim have a unique structure – caregivers will have different numbers of opportunities for attendance and participation. MRMs, however, readily accommodate this feature. The data will be structured with multiple scheduled dates for each youth/caregiver, and for each date, a value of 0 or 1 will reflect the attendance and participation status. The dichotomous attendance and participation outcomes will be modeled using a Bernoulli outcome distribution with a logit link function and Laplace approximation of the maximum likelihood function. The formulation will compare CCM and TAU on their change over time in attendance and participation. Of note, if the model building steps reveal low within-caregiver variability in attendance and participation, an unconditional level-1 model will compare CCM and TAU on the overall average level of attendance and participation.

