test for mediation and intervening variable effects reviewed by MacKinnon et al. (2002) and extended to multilevel applications by Krull and MacKinnon. For each outcome, the statistical test for mediation will be based on the estimation of two coefficients and their standard errors. These coefficients will be obtained from models that control for the level of therapeutic alliance, isolating the unique mediating effect of caregiver attendance and participation. The first coefficient (α), controlling for therapeutic alliance, represents the effect of CCM on caregiver attendance and quality of participation. The second coefficient (β), controlling for therapeutic alliance and the effect of CCM, represents the effect of caregiver attendance and quality of participation on youth drug use and antisocial behavior. Following estimation of these paths, the significance test will be conducted using asymmetric bootstrapped standard errors and confidence intervals for the product of coefficients (i.e., $\alpha \times \beta$) using the approach developed by MacKinnon and colleagues and implemented in the program PRODCLIN. Because the proposed mediators and outcomes follow longitudinal processes, a longitudinal formulation of the mediation model just described will be applied – the parallel process latent growth curve mediation model (e.g., Cheong et al.). This model will be implemented in Mplus software. Alternative longitudinal specifications, as detailed by MacKinnon, will also be considered.

Evaluation of Secondary/Exploratory Aim 4: Determine the acceptability and feasibility/disseminability challenges of the CCM parent engagement strategy and of YCM for parent participants, drug treatment providers, and JDC personnel. There are no inferential statistical analyses associated with Aim 4. Qualitative interviews will be recorded on audiotape, transcribed for analysis, and analyzed using traditional qualitative analysis (constant comparative method), in which categories and themes emerge during the analysis. The team will use a standard text retrieval and indexing software (NVivo) to facilitate the team in organizing and analyzing the data. This approach will yield conceptual dimensions rather than quantitative categories, and will highlight themes within and across interviews. At least three individuals will examine the data to permit triangulation of key themes across evaluators.

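### Aim 3 adjusts the randomised CCM-to-attendance path (α) for therapeutic alliance, which is measured only after randomisation, without stating when α×β is then a mediated effect

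*Combined protocol and SAP*

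**What the plan says.** Section 7.0, Aim 3, uses a product-of-coefficients mediation test. Both coefficients come from models that include the level of therapeutic alliance, with the stated purpose of "isolating the unique mediating effect of caregiver attendance and participation". The α coefficient, "controlling for therapeutic alliance, represents the effect of CCM on caregiver attendance and quality of participation", is multiplied by β, the attendance-to-outcome coefficient adjusted for alliance and arm. The test is an asymmetric interval for α×β. The growth-curve version inherits the adjustment, since "a longitudinal formulation of the mediation model just described will be applied".

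Section 4.0, Control Measures, gives the reason for collecting the WAI: "To control for the quality of the relationship with the therapist (CCM, TAU) as a potential confound". It also gives the timing: "The WAI will be completed monthly during active treatment".

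The Aim 1 model has no alliance term: "The formulation will compare CCM and TAU on their change over time in attendance and participation". The only further adjustment described for the mixed models is that "fixed effect indicators will be included to test for systematic differences across therapists, providers, and districts/judges", with differences controlled if found.

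**The concern.** A confounder of α would have to influence which arm a family is in. Randomisation rules that out, and a variable first measured at month 1 cannot have done so. The confounding argument can support alliance in the β model, because attendance is not randomised. It does not support alliance in the α model.

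The protocol also gives reasons why alliance might respond to CCM or to attendance. The treating therapist runs the weekly prize draw (section 5.0, Caregiver Contingency Management) and completes a WAI on the caregiver and the youth (section 5.0, Study Months 1 through 4). The same therapist is the source for session attendance: "caregiver attendance at youth treatment sessions will be recorded by therapists and measured as a percent of scheduled sessions". This link is weaker for court hearings, where supervisors or research assistants record attendance, and for the WAI versions that caregivers and youth complete.

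The Aim 3 mediation test is the interval for α×β, so an error in α passes straight into it. Aim 3 could also report an effect of CCM on attendance that disagrees with Aim 1, with no rule for reconciling the two.

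**Working it through.** The plan gives no effect size, power or expected result for Aim 3, so there is no figure to reproduce. The check covers timing first, then algebra with assumed values.

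**Timing.** Randomisation takes place with the study-entry assessments (section 3.0.4). Appendix 1 marks all four WAI versions (caregiver, youth, therapist on caregiver, therapist on youth) at months 1, 2, 3, 4 and 5, with study entry blank. The section 8.0 activities table lists five administrations of each. That makes 4 × 5 = 20 possible alliance scores per family, all after randomisation. Aim 3 does not say which is used.

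**Formula.** Let Δ be the CCM-minus-TAU difference in alliance, in within-arm SDs. Let r be the within-arm correlation of alliance with attendance propensity (SD 1). In a linear model:

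adjusted α = α − r·Δ

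- Neither CCM nor attendance changes alliance: Δ = 0, so adjusted α = α.
- Alliance follows attendance only: Δ = r·α, so adjusted α = α(1 − r²).
- CCM shifts alliance by a, with a common cause of alliance and attendance: Δ = a, so adjusted α = α − r·a.
- CCM shifts alliance by a and attendance also changes alliance: Δ = a + r·α, so adjusted α = α(1 − r²) − r·a.
- Alliance precedes attendance, no common cause: adjusted α is the net-of-alliance effect.

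**Assumed inputs.** Attendance is 40% against 60%, with random-intercept SD 1 and 16 dates, which gives α = 0.980 on the logit scale. The 40% is the family court attendance in the non-randomised study cited in section 1.0. Everything else is assumed.

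| Case | Formula | Simulated |
|---|---|---|
| Unaffected | 0.980 | 0.978 |
| Follows attendance, r = 0.3 | 0.980 × 0.91 = 0.892 | 0.892 |
| Follows attendance, r = 0.5 | 0.980 × 0.75 = 0.735 | 0.739 |
| Shift +0.3, common cause, r = 0.5 | 0.980 − 0.15 = 0.830 | 0.842 |
| Shift −0.3, common cause, r = 0.5 | 0.980 + 0.15 = 1.130 | 1.122 |
| Precedes, shift 0.3, path 0.5 (net-of-alliance effect 0.830) | 0.830 | 0.826 |
| True α = 0, shift ±0.3, common cause, r = 0.5 | ∓0.150 | −0.154, +0.146 |
| True α = 0, shift ±0.3, follows attendance (0.5), no common cause | ∓0.150 | −0.151, +0.148 |

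The last row was simulated in a linear model; the others use a random-intercept logit.

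At n = 180 the standard error of adjusted α is about 0.15 to 0.17, so the shifts from 0.98 are about 0.5 to 1.5 standard errors. With monthly WAI as a time-varying covariate most shifts are smaller (0.77 to 0.91, or 1.09).

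**Product.** Take α = 0.5, β = 0.4 and r = 0.5, so the true product is 0.200. The planned product is then:

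- follows: 0.375 × 0.4 = 0.150;
- shift +0.3, common cause: 0.35 × 0.4 = 0.140;
- shift −0.3, common cause: 0.65 × 0.4 = 0.260 (0.259 in a simulated parallel-process growth model);
- true α = 0, shift −0.3, common cause: 0.15 × 0.4 = 0.060, where the truth is 0.

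In that last case at n = 180, the 95% bootstrap interval excluded zero in 19.6% of simulated trials, against 5.3% with alliance left out of α. At r = 0.3 the figures were 9.0% and 5.7%.

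**Limit of the remedy.** Suppose attendance changes alliance (0.5) and alliance changes the outcome. The effect through attendance is 0.5 × (0.4 + 0.5 × 0.2) = 0.25 for an alliance-to-outcome effect of 0.2, and 0.5 × (0.4 + 0.5 × 0.4) = 0.30 for 0.4. Unadjusted α with alliance-adjusted β gives 0.5 × 0.4 = 0.20 in both.

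**The case against.** The strongest defence is that the adjustment is deliberate. The plan wants the incentive pathway separated from the therapist relationship, and an adjusted α can deliver a net-of-alliance effect. That is a coherent target, and it is why the adjusted product should be kept in a labelled role.

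It does not justify adjusted α as the main estimate. Alliance in the β model already separates attendance from alliance when outcomes are explained. The net-of-alliance reading also needs assumptions that the data cannot check: the +0.3 SD common-cause case and the precedes case above imply the same joint distribution of arm, alliance and attendance. Both give a product of 0.140. In the first the true value is 0.200; in the second 0.140 is the correct net-of-alliance value.

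A reader might infer that adjusted α is right only if alliance precedes attendance with no shared cause. That is too strong. It is also right when neither CCM nor attendance moves alliance, even if the two are correlated. A reader might likewise suppose that a spurious product requires a common cause. It does not: CCM shifting alliance, together with attendance changing alliance, is enough.

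It is also true that Aim 1 supplies an α without alliance, and that Aim 3 leaves alternative longitudinal specifications open. Neither says which α enters the Aim 3 product.

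**Conclusion.** The concern holds. The α model conditions on a post-randomisation variable, and the plan calls the result the effect of CCM without stating conditions under which that is so. Size and direction cannot be read from the documents, and every figure above depends on assumed values. The bias is zero if neither CCM nor attendance changes alliance.

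Two stronger readings are not supported. One is that the adjustment invalidates Aim 3 or always understates mediation. No document shows that CCM or attendance does change alliance, and the shift can go either way. The other is that the trial's main comparisons are compromised. Aims 1 and 2 carry no alliance term, and Hypothesis 3 as worded concerns the association of engagement with outcome. The point is confined to the Aim 3 mediation test, and the change is worth making before that analysis is run.

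**What to change.** 1. In the main Aim 3 model, including the latent growth version, estimate α from randomised arm, pre-randomisation covariates and any therapist, provider or district/judge indicators retained during model building. Leave alliance out, so that α agrees with Aim 1.
2. Keep alliance in the β model that enters the main product, as already planned. State that this β omits any effect of attendance that runs through alliance, and report the product with β unadjusted for alliance beside it.
3. Keep the alliance-adjusted α×β as a labelled sensitivity analysis for an effect net of alliance. State its assumptions: alliance precedes attendance, and the two share no unmeasured cause.
4. Name the WAI informant and month used.

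The change is to SAP wording; data and software stay the same. The main mediated effect will no longer be described as net of alliance. If alliance is in truth unaffected by CCM and attendance, some precision is lost: the standard error of α is about 0.19 against 0.17 at n = 180, 16 dates and r = 0.5, all but the sample size assumed. More than one estimate must be reported, and they may differ.

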3.0.4 RANDOMIZATION PROCESS

Caregivers and youth willing to participate will be consented and either complete study entry assessments and randomization or will be consented and then scheduled for an appointment for completion of study entry assessments and randomization at a more convenient time. Caregivers and youth will be randomized to either the caregiver contingency management or treatment as usual group. The proposed urn randomization procedure is a randomization method that aims to achieve balance across groups on factors that, if unaddressed, could bias estimates of the intervention effect. There is an exception to the randomization procedure. Some families will be placed into the caregiver contingency management group for the purpose of training therapists prior to receiving randomized participants.

4.0 RESEARCH DESIGN & METHODS Design Overview:

A well-specified intervention, Contingency Management, will be adapted to reinforce caregiver participation in drug court (CCM). We propose a randomized clinical trial examining the utility of caregiver contingency management to increase caregiver engagement in juvenile drug court and adolescent drug treatment activities. The proposed study follows a 2 (treatment type: Drug Court plus treatment as usual (TAU); Drug Court and TAU plus Caregiver CM [CCM] x 10 (time: pretreatment [T0], 1-month [T1], 2-month [T2], 3-months [T3], 4-month [T4], 5-month [T5], 6-months [T6], 9-months [T7], 12-months [T8], and 18-months [T9-six months post-juvenile drug court involvement]) factorial design, with random assignment of 180 caregivers/youths to one of the two treatment conditions. Repeated measures of caregiver and youth functioning will be collected at pre-treatment (T0), and each of the post-randomization time points (T1 – T9). We choose a randomized trial because this is the most valid way to test the efficacy of our proposed intervention. We choose the follow-up time line to measure short-term and long-term maintenance of change. Our randomization procedure will help mitigate bias across the treatment groups, providing groups that are equally distributed across a number of characteristics known to influence outcomes.

Study Timeline:

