Additional Measures. These instruments will be used to describe the sample; some will be examined in supplemental analyses as possible moderators of outcomes. (1) **Demographics and Service**

Version: 2017 09 06 Page 13 of 45

Utilization Survey completed by caregivers and Demographics forms completed by therapists, youth, and drug court personnel, (2) The presence of substance use disorders and specific psychiatric comorbidities (e.g., anxiety, mood, disruptive behavior disorders) will be assessed by research staff using scales from the Global Appraisal of Individual Needs-Initial (GAIN-I), (3) The self-report version of the Addiction Severity Index (ASI), (4) The widely-used 21-item Beck Depression Inventory-2nd Edition (BDI-II) will assess caregiver depression, (5) Homework Rating Scale will assess parent compliance with homework, (6) Parent-Adolescent Sexual Communication scale will assess parent and adolescent perception of the quality and quantity of sexual communication, (7) Termination Questionnaire will provide information about why a family left treatment and will be completed by study therapists, and (8) Choice Questionnaire (Kirby Delay Discounting) measure, will provide information about impulsive choice — a personal characteristic CM interventions attempt to augment.

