5.0 STUDY ACTIVITIES

Study Entry Assessment (Time 0). Research assistants will meet with families at an agreed upon location to complete study entry assessments. During this assessment, youth will provide demographic information and complete interviews and questionnaires that assess substance use (Brief Problem Checklist, Global Appraisal of Individual Needs), mental health symptoms (Brief Problem Checklist, Self-Report of Delinquency, Global Appraisal of Individual Needs), criminal activity (Self-Report Delinquency), sexual behavior (demographics form), sexual communication patterns with their caregiver (Parent-Adolescent Sexual Communication – Adolescent Version) and impulsivity (Choice Questionnaire); and the teen's most urine drug screen results to the study entry assessment date will be obtained from probation.

At the same visit, caregivers will provide demographic information and service utilization history; complete interviews and questionnaires about their teen's behavior (Child Behavior Checklist), mental health symptoms (Child Behavior Checklist), impulsivity (Choice Questionnaire); and their own perception of incentive programs (Perception of Incentive Programs). Parents will also provide information about their own substance use history (Addiction Severity Index), mental health symptoms (Beck Depression Inventory), and communication patterns with their child about sex (Parent-Adolescent Sexual Communication – Caregiver Version)

Research assistants will meet with juvenile drug court personnel at juvenile probation offices to have juvenile drug court personnel provide demographic information and complete a questionnaire about their perception of incentive programs (Perceptions of Incentive Programs).

Selected therapists will provide demographic information and complete a questionnaire about their perception of incentive programs (Perceptions of Incentive Program). This information will be collected by research assistants prior to therapist's training.

Study Months 1 through 4. During study months 1-4, caregivers in the CCM group will engage in treatment as they normally would plus the prize-based contingency management intervention with the therapist at the provider agency. Caregivers in the TAU group will engage in treatment as they normally would with the therapist at the provider agency only.

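### The Aim 3 engagement-to-outcome path (β) is not randomised, is adjusted only for alliance and arm, and leaves out study-entry risk factors that the trial collects, so shared risk can be reported as mediation

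*Combined protocol and SAP*

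**What the plan says.** Section 7.0, Aim 3, rests the mediation test on two coefficients. α is the effect of CCM on engagement, controlling for alliance. For β: "The second coefficient (β), controlling for therapeutic alliance and the effect of CCM, represents the effect of caregiver attendance and quality of participation" (outcomes: youth drug use and antisocial behaviour). Both come from "models that control for the level of therapeutic alliance, isolating the unique mediating effect of caregiver attendance and participation". The test is a confidence interval for α × β. A parallel process latent growth model is then described as a longitudinal formulation of the same mediation model, with no covariates added. Alternative longitudinal specifications may also be considered.

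The Aim 3 text names no study-entry covariate for β, no no-confounding assumption and no sensitivity analysis.

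Four other places bear on the point:

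- **What is randomised.** Section 4.0, Design Overview, provides for "random assignment of 180 caregivers/youths to one of the two treatment conditions". Section 3.0.4 says that the urn procedure "aims to achieve balance across groups on factors that, if unaddressed, could bias estimates of the intervention effect".
- **What is measured at entry.** Section 5.0, Study Entry Assessment: "Parents will also provide information about their own substance use history (Addiction Severity Index), mental health symptoms (Beck Depression Inventory"). Caregivers also complete the Child Behavior Checklist, and youth complete the GAIN and the Self-Report Delinquency Scale. Appendix 1 confirms these at study entry.
- **What those measures are for.** Section 4.0, Additional Measures, lists the caregiver depression and addiction scales and the GAIN-I diagnostic scales: "These instruments will be used to describe the sample; some will be examined in supplemental analyses as possible moderators of outcomes". The Child Behavior Checklist and GAIN subscales also appear as outcome measures. None is assigned to the β model.
- **Other controls.** Section 7.0, Model building, tests therapist, provider and district/judge indicators and keeps them if differences are found. Section 4.0, Control Measures, says that outside services will be assessed and controlled for, and schedules the alliance measure monthly during active treatment.

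**The concern.** Randomisation makes the comparison of arms fair, so it protects α and the total effect of CCM. It does nothing for the comparison of highly engaged with poorly engaged caregivers within an arm, and that comparison is what estimates β.

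The protocol's own background makes a common cause plausible. Section 1.0 says that the strain of managing a difficult child can erode caregivers' motivation, and that family variables help to cause and sustain adolescent substance abuse. Section 4.0 already treats alliance as a possible confounder, so the principle is accepted. But alliance is measured after randomisation and does not represent pre-treatment risk.

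If CCM does raise engagement, as Hypothesis 1 predicts, the mediation verdict rests almost wholly on β. Aim 3 could then report that engagement explains a youth benefit when engagement has no effect on youth outcomes. That is the claim on which wider use of caregiver incentives would be justified.

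**Working it through.** Section 7.0 gives no effect size, power or error rate for Aim 3, so there is no stated figure to reproduce. What follows is illustrative.

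**From the documents:** 180 families, two arms, β adjusted for alliance and arm, an asymmetric product interval. The 95% level is stated for the mixed models and assumed for α × β.

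**Assumed:** 90 per arm; true β = 0; a CCM effect on engagement of d = 0.3, 0.5 or 0.8 SD; one entry factor U that correlates −r with engagement (M) and +r with the youth outcome (Y); U correlates 0.2 with alliance.

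**Step 1, approximate size of the bias.** Within arm, Var(M) = 1 and Cov(M, Y) = −r × r, so omitting U gives a spurious β of about −r²: −0.04, −0.09 and −0.16 at r = 0.2, 0.3 and 0.4. The standard error is about 1/√(180 − 4) = 0.075. The shift in the test statistic is then 0.04/0.075 = 0.53, 0.09/0.075 = 1.20 and 0.16/0.075 = 2.13. A two-sided 5% test of β rejects in about 8%, 22% and 57% of trials.

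**Step 2, cross-sectional simulation** (2,000 trials per cell). Percentage of trials declaring mediation with the planned adjustment, and in brackets after U is added to both regressions:

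| d | r = 0 | r = 0.2 | r = 0.3 | r = 0.4 | r = 0.5 |
|---|---|---|---|---|---|
| 0.3 | 1.8 (1.9) | 3.1 (1.8) | 8.4 (2.0) | 26.2 (2.4) | 44.1 (3.1) |
| 0.5 | 4.6 (4.8) | 6.4 (4.4) | 18.9 (5.0) | 46.2 (4.5) | 81.2 (4.8) |
| 0.8 | 5.6 (5.6) | 9.8 (6.4) | 19.8 (5.8) | 55.4 (6.0) | 90.0 (4.4) |

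The mean spurious β at d = 0.5 is −0.039, −0.088, −0.153 and −0.244 for r = 0.2 to 0.5, close to −r². Power for α with 90 per arm is 52%, 92% and over 99% at d = 0.3, 0.5 and 0.8, which is why the d = 0.3 row is lower. Runs without alliance in the model are somewhat higher. Across all runs with d = 0.5–0.8, the ranges are 6–10%, 19–25% and 46–62% at r = 0.2, 0.3 and 0.4, and about 4–8% after adjustment. If U is measured with reliability 0.8 (d = 0.5, r = 0.4), adjustment takes the rate from 49.8% to 6.8%.

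**Step 3, the outcome as change over time.** The plan also models growth, with GAIN and SRD at months 0, 3, 6, 9, 12 and 18. A stand-in used each youth's fitted slope as the outcome, with assumed level SD 1, slope SD 0.5 and residual SD 0.7, alliance omitted, r = 0.4 and d = 0.5–0.8:

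- U shifts level only: about 5%.
- U correlates r/2 with the true slope: 8–11%.
- U correlates r with the true slope: 18–23%. At r = 0.3 this case gives 9–10%.
- Other variance assumptions, U acting on the rate of change at r = 0.4: 33–39%.

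The third line can be checked by hand. With 18 months as one time unit, the six times have a sum of squared deviations of 0.648. The reliability of a fitted slope is 0.25/(0.25 + 0.49/0.648) = 0.25, with square root 0.50. The shift is 0.16 × 0.50/0.075 = 1.07, which gives about 19%.

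**Step 4, cost of an arm-specific β.** Letting β differ by arm raises the CCM-arm standard error from 0.076 to 0.107, a ratio of 0.107/0.076 = 1.41, because half the families estimate it. With a common true β and d = 0.5, mediation power falls from 70% to 41% at β = 0.2 and from 90% to 73% at β = 0.3.

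**The case against.** The strongest reply is that the cross-sectional figures do not describe the planned growth model. This stands. A factor that only shifts the level of drug use goes into the intercept and causes no false mediation of the slope. A reader might take 46–62% as the plan's error rate, but the documents do not support that. They give no correlation between entry risk and engagement or outcome, and no variance components. Nor do they show that more engaged caregivers differ at entry; that is plausible, not established. A confounded β can make the product significant but need not: at r = 0.2 the inflation is small.

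Second, the plan is not bare of other controls. Provider, therapist and judge effects enter if differences are found, and outside services are to be controlled. This also stands, and the statement that β is adjusted only for alliance and arm is true of the Aim 3 text, not of all Section 7.0. Neither control covers caregiver depression, caregiver addiction severity or the youth's severity at entry.

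Third, Hypothesis 3 speaks only of association. But Aim 3 asks whether engagement explains the changes, and the analysis text speaks of a unique mediating effect. Those words need the missing assumption.

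Finally, a reader might infer that β must be allowed to differ between arms because attendance rewarded with prizes may act differently. The documents give no arm-specific values from which to size such a difference, and Step 4 shows a substantial loss of precision. It does not belong in the main model.

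**Conclusion.** The point holds. As written, the β path is observational, is adjusted for a post-randomisation covariate and arm, with provider-type effects only conditionally, and is given an interpretation that needs an unstated assumption. Measured entry factors that would reduce the bias are left out.

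The size is uncertain because every correlation and variance is assumed. The problem is small at r = 0.2. In a cross-sectional model it is material from r = 0.3 when CCM's effect on engagement is moderate or larger. In the growth model it depends on whether entry risk predicts the rate of change: at r = 0.4, from no inflation up to about 39%.

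Aims 1 and 2 are not affected, since they compare randomised arms. Adjustment for measured factors reduces the confounding but cannot exclude what is unmeasured.

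**What to change.** In Section 7.0, Aim 3, before analysis:

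1. Pre-specify study-entry caregiver BDI-II, caregiver ASI, Child Behavior Checklist, youth GAIN severity and provider as covariates in the β model, and also in the α model. Provider should enter unconditionally here.
2. In the parallel process model, regress both the outcome slope and the engagement growth factors on these covariates. Where the baseline outcome is already the month-0 repeated measure, as with GAIN, let its intercept predict the slope instead of entering it a second time.
3. Add a sensitivity analysis showing how large a residual mediator-outcome correlation would remove the indirect effect.
4. Replace the claim of isolating a unique mediating effect with wording conditional on no unmeasured mediator-outcome confounding.
5. If wanted, report a CCM × engagement interaction as a secondary sensitivity analysis only, since it widens the CCM-arm β standard error by about 40%.

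No new data are needed. The cost is a text change, a few degrees of freedom among 180 families and a more cautious Aim 3 statement.
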